3 SYNOPSIS

Protocol Number:

TLC590A1001

Title:

A Phase I/II, Randomized, Double-blind, Comparator-controlled, Dose-escalation Study to Evaluate the Safety, Pharmacokinetics, and Efficacy of TLC590 for Postsurgical Pain Management Following Inguinal Hernia Repair

Investigational Product:

TLC590 (Ropivacaine Liposome Injectable Suspension)

Study Centers:

Approximately 2 centers in the United States (US)

Phase:

Phase I/II

Objectives:

The primary objective of this study is to evaluate the safety and tolerability of TLC590 for postsurgical pain management in subjects with inguinal hernia repair surgery.

The secondary objectives of this study are:

- To evaluate the pharmacokinetic (PK) profile and dose-exposure relationship of TLC590, as well as the bioavailability as compared with Naropin®.
- To evaluate analgesic efficacy of TLC590 compared with Naropin® for postsurgical pain management in subjects with inguinal hernia repair surgery.
- To evaluate the exposure-response relationship between PK parameters and pain management.

Study Design:

This is a Phase I/II, randomized, double-blind, comparator-controlled, dose-escalation study to assess the safety, PK, and efficacy of single postsurgical application of TLC590 compared with Naropin® via a single infiltrative local administration in adult subjects following inguinal hernia repair surgery.

The study will enroll approximately 64 evaluable subjects who meet all entry criteria across 4 cohorts.

Approximately 16 subjects will be enrolled to each cohort in a 3:1 ratio. Each cohort will comprise 12 subjects receiving a dose of TLC590 and 4 subjects receiving active comparator drug (Naropin® 150 mg; [0.5%, 5 mg/mL]) in accordance with the randomization schedule (as assigned by a centralized interactive web response system [IWRS]) and dose-escalation scheme outlined in the following table.

Cohort	TLC590	Naropin®
Cohort 1 (N = 16)	N = 12: TLC590; 190 mg (10 mL)	N = 4: Naropin®; 150 mg (30 mL)
Cohort 2 (N = 16)	N = 12: TLC590; 380 mg (20 mL)	N = 4: Naropin®; 150 mg (30 mL)
Cohort 3 (N = 16)	N = 12: TLC590; 570 mg (30 mL)	N = 4: Naropin®; 150 mg (30 mL)
Cohort 4 (N = 16)	N = 12: TLC590; 760 mg (40 mL) OR N = 12: TLC590; 475 mg (25 mL); if the TLC590 570 mg (30 mL) dose is not tolerated	N = 4: Naropin®; 150 mg (30 mL)

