Dose escalation of a single postsurgical administration of TLC590 will be performed using sequential dose levels starting at 190 mg up to 760 mg, as compared with Naropin® 150 mg (5 mg/mL) via infiltrative local administration in adult subjects following unilateral Lichtenstein inguinal hernia repair surgery. Dose escalation

will be determined by review of treatment-related adverse events and all serious AEs (SAEs) by a safety monitoring committee (SMC); PK data will also be reviewed only by the SMC at the end of each cohort to assess systemic exposure to total and free (unbound) ropivacaine.

Number of Subjects:

Approximately 64 evaluable subjects in up to 4 cohorts of approximately 16 subjects per cohort will be enrolled in this study.

Treatment:

At the end of the surgery, prior to wound closure, a single infiltrative local dose of blinded study medication will be administered.

Study Duration:

The study duration will be approximately 60 days. Each subject will be screened within 28 days before blinded study medication administration. At the end of the surgery, prior to wound closure, a single infiltrative local dose of blinded study medication will be administered. The subject will remain in the clinic at least 48 hours after administration of blinded study medication, and each subject will be followed for 30 days.

Study Population:

Inclusion Criteria:

To be eligible for study entry, subjects must satisfy all of the following criteria:

1. Able and willing to provide a written informed consent, indicating that he/she is aware of the investigational nature of this study involved and willing to comply with the requirements of this study protocol.
2. Male or female between 18 and 65 years of age, inclusive.
3. Scheduled to undergo a primary, unilateral Lichtenstein inguinal hernia repair with mesh, and be able to use the anesthesia regimen.
4. Have an American Society of Anesthesiology (ASA) Physical Status Classification of 1 or 2.
5. Female subjects are eligible only if all of the following apply:
 - Not pregnant (female subjects of childbearing potential must have a negative serum pregnancy test at Screening and negative urine pregnancy test at Baseline before randomization);
 - Not lactating;
 - Not planning to become pregnant during the study;

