The Kaplan-Meier method will be used to analyze time to the first postoperative use of rescue analgesic, and time to the first postoperative use of rescue opioid. Comparison of the survival curves among treatments will be assessed by a log-rank test.

Chi-square test or Fisher's exact test will be used to assess the overall differences among treatments for the proportions of subject who are opioid free, subjects who used no rescue analgesics, and subjects who used no postoperative antiemetic therapy, and PGA.

All the exploratory endpoints will be summarized descriptively.

Blood concentrations of ropivacaine (unbound and total) will be descriptively summarized at each scheduled time of PK sampling by treatment. PK parameters will be derived by non-compartmental analysis.

The dose-exposure relationship of TLC590 will be evaluated by the tabulation of AUC and C_{max} parameters obtained from each dose level and displayed graphically. The power model will be used to investigate the dose proportionality for subjects who received the TLC590 treatment. The relative systemic bioavailability (including relative AUC and C_{max}) compared to Naropin[®] will be analyzed by using a general linear model (GLM). Exposure-response relationship between PK parameters and NPRS scores will be displayed graphically and will be evaluated accordingly.

Safety analysis will be based on all safety information collected including physical examination, surgical site assessment, vital signs assessments, clinical laboratory data, 12-lead electrocardiogram (ECG), AEs, and SAEs.

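### Does the Naropin bioavailability comparison need a stated dose adjustment, given that no TLC590 dose equals 150 mg?

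*Combined protocol and SAP*

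**What the plan says.** The Objectives in section 3 (Synopsis) list, among the secondary aims, the PK profile and dose-exposure relationship of TLC590, "as well as the bioavailability as compared with Naropin".

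The Study Design part fixes Naropin at 150 mg (30 mL at 5 mg/mL) in every cohort, with 4 Naropin and 12 TLC590 subjects per cohort. TLC590 is given at 190, 380 and 570 mg in cohorts 1 to 3, and at 760 mg, or alternatively 475 mg, in cohort 4. The text sums this up as "sequential dose levels starting at 190 mg up to 760 mg, as compared with Naropin® 150 mg (5 mg/mL".

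The Statistical Analysis part gives two separate sentences on the PK models. On dose: "The power model will be used to investigate the dose proportionality for subjects who received the TLC590 treatment". On the comparator: "The relative systemic bioavailability (including relative AUC and C_{max}) compared to Naropin[®] will be analyzed by using a general linear model (GLM". The synopsis does not connect them, and it does not mention dose normalisation, the log scale, the model terms, or whether the ratio is per dose or pooled.

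**The concern.** With one comparator dose and no TLC590 dose equal to it, a raw exposure ratio mixes the effect of the formulation with the effect of giving more drug. Dividing by dose removes the second effect only if exposure is proportional to dose from 150 mg up to the TLC590 dose compared. The plan treats proportionality as an open question, to be examined in TLC590 subjects alone.

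Three choices therefore seem to be left until the data are in: raw or normalised, per dose or pooled, and what to report if the power-model slope is not 1. If the choice or its label were made after seeing results, a dose effect could be presented as incomplete or excess release from the liposome. Bioavailability against Naropin is a named secondary objective, so the question was worth checking.

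**Working it through.** **Inputs from the synopsis.** Naropin: 30 mL x 5 mg/mL = 150 mg, as stated. Subjects: 4 x (12 + 4) = 64, as stated, so 48 TLC590 and 16 Naropin. The slope b and the between-subject CV are not given; the values below are assumptions. All 64 subjects are taken as evaluable for PK, and both products' doses as expressed on the same mg basis.

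**1. Does silence on normalisation matter at a given dose?** The dose ratios D/150 are 1.27 (190 mg), 2.53 (380), 3.17 (475), 3.80 (570) and 5.07 (760). For a single TLC590 dose D,

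ln(AUC/D) - ln(AUC_Naropin/150) = [ln AUC - ln AUC_Naropin] + ln(150/D).

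The last term is a constant. With each dose group as a level of the model, the residuals, the standard error and the width of the log-scale interval are the same either way. For example, with a true relative bioavailability of 0.80 and proportional exposure, the raw ratio is 0.80 x 190/150 = 1.01 at 190 mg and 0.80 x 760/150 = 4.05 at 760 mg. Multiplying by 150/190 and 150/760 returns 0.80 in both cases. Any reader with the dose table can convert one into the other.

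**2. What if AUC is not proportional to dose?** Let TLC590 AUC be proportional to dose^b, with 100% relative bioavailability at 150 mg. The normalised ratio at dose D is then (D/150)^(b-1):

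| Dose (mg) | b = 0.8 | b = 1.2 |
|---|---|---|
| 190 | 0.954 | 1.048 |
| 380 | 0.830 | 1.204 |
| 475 | 0.794 | 1.259 |
| 570 | 0.766 | 1.306 |
| 760 | 0.723 | 1.383 |

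Pooling over 190, 380, 570 and 760 mg (geometric mean dose 420.5 mg) gives 0.814 and 1.229. A pooled ratio would depend on the dose mix; ratios by dose would show the trend openly. At 190 mg the departure is at most 5%. Sampling error there is larger: with 12 against 16 subjects the standard error of the log ratio is s x sqrt(1/12 + 1/16) = 0.382s, where s = sqrt(ln(1 + CV^2)). At a CV of 30%, s = 0.294, and the 90% interval spans a factor of exp(1.706 x 0.382 x 0.294) = 1.21 either way. These figures concern AUC only; Cmax also depends on absorption rate.

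**3. Would a rule tied to the power model do better?** The natural candidate is to switch, when proportionality is not supported, to TLC590 AUC predicted at 150 mg over Naropin AUC observed at 150 mg. The sum of squares of ln(dose) about its mean, 12 subjects per dose at 190, 380, 570 and 760 mg, is 13.01.

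- Standard error of the predicted contrast: s x sqrt(1/48 + (ln 150 - ln 420.5)^2/13.01 + 1/16) = 0.406s.
- Against the single-dose contrast: 0.406/0.382 = 1.06.
- Against the pooled normalised contrast, s x sqrt(1/48 + 1/16) = 0.289s: 0.406/0.289 = 1.41, or 41% more.
- The 90% half-width for b is 1.679 x s/sqrt(13.01): 0.137 at a CV of 30%, and 0.258 at 60% (s = 0.555).

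The trigger is fragile. One common criterion asks for the 90% interval of b to lie within 1 ± ln 1.25/ln 4, that is 0.839 to 1.161. With true b = 1, it is met about 24% of the time at a CV of 30% and practically never at 60%, since 0.258 exceeds 0.161. If instead the switch occurs when the interval excludes 1, a true slope of 1.2 is detected only about 36% of the time at a CV of 60%.

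**The case for a change.** The strongest case for a change is that the estimate for a named objective should be fixed beforehand, that the remedy is only wording, and that the slope may well be too imprecise to settle proportionality. At 760 mg the half-widths above amount to a factor of 5.067^0.137 = 1.25 to 5.067^0.258 = 1.52. An inconclusive slope leaves room to choose between raw and normalised ratios, or between pooled and per-dose ratios, once the results are known.

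Part of this stands. The synopsis is silent on these points, no dose matches, and a pooled ratio would be hard to interpret if the slope departed from 1.

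The rest does not. The design does separate dose from formulation to a useful degree, because four TLC590 levels estimate the dose effect within the product. A ratio of 72% at 760 mg is also not necessarily wrong. If ropivacaine clearance is constant and the liposome releases a smaller fraction at higher doses, 72% is the relative bioavailability at 760 mg. It misleads only if clearance itself changes with exposure, and a slope from TLC590 subjects alone cannot tell the two apart. The dose-matched alternative describes 150 mg of TLC590, which nobody receives, and leans on the fitted line over all doses, so curvature at the upper doses would shift it.

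**Conclusion.** No change is called for. The omission is real, but it is the kind of detail that a synopsis leaves out and a PK analyst supplies in the usual way: log-transformed AUC and Cmax divided by dose, a geometric mean ratio with interval for each TLC590 dose against Naropin, and raw ratios shown as relative exposure. Carried out like that, the planned GLM gives a sound estimate, and the planned power model sits beside it to show whether the ratio drifts with dose.

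The possible drift is at most 5% at 190 mg and runs from 72% to 138% at 760 mg, for assumed slopes of 0.8 to 1.2 and for AUC only. It would be visible in ratios by dose, and it may be a true property of the product. The one substantive alternative, a conditional ratio at 150 mg, is a debatable trade: 6% more standard error than a single-dose contrast, 41% more than the pooled one, and a trigger that depends heavily on the criterion chosen.

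The consequence is small. The objective is secondary and the study has no formal sample size. Under the synopsis, escalation rests on the safety monitoring committee's review of adverse events, with exposure data reviewed by that committee directly; it ties no decision to this ratio. The assessment rests on the synopsis; if the body of the plan states the normalisation, the question does not arise.
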